### **5.9.1 Complete Response Rate**

CRR is defined as the proportion of patients with a best overall response (BOR) of complete response (CR). CRR is according to the 2014 Lugano classification (Cheson et al., 2014) as determined by the IRC (Phase 2 only) and the investigator (both Phase 1 and Phase 2).

The CRR and its 95% two-sided exact CIs will be presented by the IRC and the investigator, respectively.

### **5.9.2 Overall Response Rate**

Overall response rate (ORR) is defined as the proportion of patients with a BOR of CR or partial response (PR). ORR is according to the 2014 Lugano classification as determined by IRC (Phase 2 only) and the investigator (both Phase 1 and Phase 2).

For the analysis of ORR,

- The category of BOR includes complete response (CR), partial response (PR), stable disease (SD), progressive disease (PD), and inevaluable (NE).
- Overall responses derived for BOR must be assessed on or before the start of subsequent anti-cancer therapy or procedure.
- A BOR of SD requires the patient on-study for a minimum of 35 days after the first dose of study drug. A patient with SD only before this time will be considered as NE.
- For patients who do not have post-baseline assessment due to early clinical progression or death (after receiving study drug), they will be categorized separately from patients with assessments.

Disease control rate (DCR) is defined as the proportion of patients with a BOR of CR, PR, or SD.

The ORR and DCR and their 95% two-sided exact CIs will be presented by the IRC and the investigator, respectively.

Percent change from baseline in the sum of product of the perpendicular diameters (SPD) for target lesions will be presented and also displayed as a waterfall plot, with vertical bars representing the sorted values of best percent reduction for each patient.

### **5.9.3 Duration of Response**

Duration of response (DoR) is defined among patients with a BOR of CR or PR as the time from the documentation of first tumor response to either disease progression (based on

radiographic or clinical progression at end of treatment [EOT]/end of study [EOS]) or death due to any cause, whichever occurs first.

The censoring rules for DoR are as follow:

- For patients who are still alive at the time of analysis and without objective evidence of progression, patients will be censored at the last tumor assessment.
- For patients who receive subsequent anti-cancer therapy or procedure prior to disease progression or death, patients will be censored at the last tumor assessment prior to subsequent therapy or procedure.
- A sensitivity analysis might be considered: if a clinical progression or toxicity is observed without radiologic progression assessment confirmed, then the patient will be censored at the last tumor assessment.

The DoR will be estimated by Kaplan-Meier method. The median DoR and its 95% two-sided CI will be presented by the IRC and the investigator, respectively.

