8.1 Efficacy Assessments

Disease assessments will occur as per the SoE ([Table 1](#) and [Table 2](#)) until progression. Disease assessments should take place at the time points specified even if dosing of study drug(s) is delayed. Additional disease assessments may be obtained, if clinically indicated.

Clinical examination for lymphoma will be performed at all disease assessment time points. Positron emission tomography-computed tomography (PET-CT) of the neck/chest/abdomen/pelvis and other areas of known disease or newly suspected disease, will be performed at baseline. Patients with PET-avid disease at baseline should have PET-CT for all subsequent disease assessments. If disease is not PET-avid at baseline, computed tomography (CT) with contrast or magnetic resonance imaging (MRI) must be used for subsequent disease assessments.

Images for all patients treated during the Phase 2 portion of the study will be submitted for central review. Submission instructions for central review will be provided in a separate manual. Central imaging review will be performed using two blinded independent reviewers with adjudication by a third blinded independent reviewer in cases of discordance.

Screening (Baseline) imaging must be performed within 4 weeks prior to C1D1.

During the Treatment Period, imaging will be performed 6 weeks and 14 weeks after C1D1, then every 8 weeks until EOT. Week 6 imaging should be performed prior to C3D1 and Week 14 imaging should be performed prior to C5D1. All other imaging should be performed within \pm 2 weeks of the scheduled time point. Disease assessments should be performed at the time points specified even if study drug dosing is delayed. If a scan has been performed within 8 weeks of EOT, it does not need to be repeated at EOT.

During the Follow-up Period, patients who discontinued study drug(s) for reasons other than disease progression or initiation of other anti-cancer therapy except stem cell transplant, will have imaging performed every 12 (\pm 2) weeks until 1 year from EOT, then every 6 months until disease progression, up to 2 years from EOT.

Response data will be collected for patients who receive CAR-T therapy until 90 days after receiving CAR-T therapy.

If a scan has been performed within 8 weeks of EOT, it does not need to be repeated at EOT.

In case of dose delays, disease assessment should be maintained at the frequencies defined above.

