9.7.5 Progression-free Survival

PFS will be defined as the time from first dose of study drug until the first date of either disease progression or death due to any cause. For patients whose disease has not progressed at the time of the analysis, censoring will be performed using the date of the last valid disease assessment. The data will be analyzed by the Kaplan-Meier method. The median PFS time and 95% CI will be presented. Further details will be outlined in the SAP.

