## **4.3 Modifications to the statistical section of the protocol**

Not applicable.

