#### **5.9.4 Relapse-Free Survival**

Relapse-Free Survival (RFS) is defined as the time from the documentation of CR to either disease progression (based on radiographic or clinical progression at EOT/EOS) or death due to any cause, whichever occurs first.

The censoring rules for DoR apply to RFS.

The RFS will be estimated by Kaplan-Meier method. The median RFS and its 95% two-sided CI will be presented by the IRC and the investigator, respectively.

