#### **5.9.5 Progression-Free Survival**

Progression-Free Survival (PFS) is defined as the time from first dose of study drug until either disease progression (based on radiographic or clinical progression at EOT/EOS) or death due to any cause, whichever occurs first.

The censoring rules for PFS are as follow:

- For patients who are still alive at the time of analysis and without objective evidence of progression, patients will be censored at the last tumor assessment.
- For patients who receive subsequent anti-cancer therapy or procedure prior to disease progression or death, patients will be censored at the last tumor assessment on or prior to subsequent therapy or procedure.
- For patients have no post baseline tumor assessment, and have no disease progression or death, or receive subsequent anti-cancer therapy or procedure, patients will be censored at the first dose date of study drug.

- A sensitivity analysis might be considered: if a clinical progression or toxicity is observed without radiologic progression assessment confirmed, then the patient will be censored at the last tumor assessment.

The PFS will be estimated by Kaplan-Meier method. The median PFS and its 95% two-sided CI will be presented by the IRC and the investigator, respectively.

A swimmer plot will be displayed, including the points at which the criteria for response and progression by a specific manifestation were met (such as CR, PR, SD, PD, death, and stem cell transplant etc.).

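### DoR and RFS censoring in the SAP can give a negative duration when response is documented on the day new therapy starts, and no planned analysis follows patients through stem cell transplant

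*SAP*

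**What the plan says.** **New-therapy rule in the SAP.** For DoR (SAP 5.9.3), if a subsequent anti-cancer therapy or procedure comes before progression or death, "patients will be censored at the last tumor assessment prior to subsequent therapy or procedure". SAP 5.9.4 states "The censoring rules for DoR apply to RFS". For PFS (SAP 5.9.5) the corresponding rule is "patients will be censored at the last tumor assessment on or prior to subsequent therapy or procedure". SAP 5.8.2 counts transplant among the subsequent therapies and procedures, and none of the three rules makes an exception for it.

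**Response window in the SAP.** SAP 5.9.2 states "Overall responses derived for BOR must be assessed on or before the start of subsequent anti-cancer therapy or procedure". DoR starts at the first documented response and RFS at the documented CR.

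**Protocol.** Sections 9.7.3 and 9.7.4 count the first progression or death from any cause and censor only patients with neither event, at the last valid assessment. Section 9.7.5 does the same for PFS, its rule applying to anyone "whose disease has not progressed at the time of the analysis, censoring will be performed using the date of the last valid disease assessment". None of the three mentions new therapy, and each leaves further details to the SAP. Sections 9.7.1 and 9.7.2 do apply a new-therapy cut-off, but to response only.

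**Imaging.** Protocol 8.1 describes follow-up scans for patients who stopped study drug for reasons other than progression or "initiation of other anti-cancer therapy except stem cell transplant, will have imaging performed". Scans therefore continue after stem cell transplant and stop after other new anti-cancer therapy. Protocol 7.1 lists transplant as a reason for ending study treatment.

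**Record of changes.** Under the heading "Modifications to the statistical section of the protocol", SAP 4.3 says only that the item is not applicable.

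**The concern.** There are two separate problems.

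The first is a boundary error. The response window and the PFS rule include the start day of the new therapy; the DoR and RFS rules exclude it. A scan on that day can make the patient a responder and start the DoR clock, yet it cannot serve as the censoring date. The censoring date then falls before the start date, and a program written to the SAP would produce an impossible value or need an undocumented repair.

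The second is how transplant is handled. A progression or death after transplant is an event under the text of protocol 9.7.3 to 9.7.5 and a censored observation under the SAP. Patients sent to transplant are probably in response, so the censoring may be related to prognosis. The protocol schedules the scans needed to see what happens to these patients, but no planned Kaplan-Meier estimate uses them. The one sensitivity analysis that the SAP mentions is optional and addresses clinical progression or toxicity without radiologic confirmation.

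**Working it through.** The documents give no sample size, power or event figure for DoR, RFS or PFS, so there is no plan figure to reproduce.

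**Step 1. The start day of new therapy under each rule**

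| Quantity | Scan on the start day of new therapy |
|---|---|
| Best overall response, SAP 5.9.2 | counts |
| PFS censoring, SAP 5.9.5 | counts |
| DoR censoring, SAP 5.9.3 | does not count |
| RFS censoring, SAP 5.9.4 | does not count |

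**Step 2. Day arithmetic for the boundary case**

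Protocol 8.1 places scans at weeks 6 and 14 and then every 8 weeks. With C1D1 as day 1, the nominal days are 43, 99, 155 and 211. Suppose the first response is documented on the day the new therapy starts. Then DoR = (last scan strictly before that day) - (day of first response).

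- First response at day 99: 43 - 99 = -56 days.
- At day 155: 99 - 155 = -56 days. At day 211: 155 - 211 = -56 days.
- At day 43, only the baseline scan is earlier. Taking it between day -27 and day -1 gives -27 - 43 = -70 to -1 - 43 = -44 days.

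Adding one day, a common convention, changes -56 to -55. RFS is negative in the same way when the first CR falls on that day. PFS is not affected: it starts at first dose and its rule includes the day. With the PFS wording, DoR becomes 0 days (1 day with the convention).

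**Step 3. Illustration of the transplant rule for DoR**

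Inputs: a median DoR of 10.25 months, the monotherapy figure in protocol 1.2.2.2, with an exponential distribution. Assumed, with no source in the documents: a share s of responders transplanted, transplant 3 months after response, and a hazard multiplied by h after transplant.

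λ = ln 2 / 10.25 = 0.0676 per month.

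For t > 3, following patients through transplant: S(t) = (1 - s)·exp(-λt) + s·exp(-3λ - hλ(t - 3)). Solve S(t) = 0.5.

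| s | h = 0.5 | h = 1 | h = 1.5 |
|---|---|---|---|
| 10% | 10.68 | 10.25 | 9.94 |
| 20% | 11.16 | 10.25 | 9.64 |
| 30% | 11.69 | 10.25 | 9.37 |

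Censoring at transplant gives 10.25 months in every cell. The largest shifts are 11.69 - 10.25 = 1.44 months up and 10.25 - 9.37 = 0.88 months down. At h = 0.25 the medians are 10.97, 11.83 and 12.89 months.

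**Step 4. Scale against sampling error**

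SAP 4.1 gives 49 + 30 = 79 DLBCL patients in Phase 2. At the interim ORR of 57.1% in all DLBCL (protocol 2.2), that is 79 × 0.571 ≈ 45 responders. The approximate 95% interval for an exponential median is 10.25 × exp(±1.96/√d). Assuming d = 20 events gives 6.6 to 15.9 months; d = 45 gives 7.7 to 13.7 months. Every shift in step 3 lies inside both intervals.

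**The case against.** A reader might infer that the SAP contradicts the protocol. The documents do not support that. Protocol 9.7.3 to 9.7.5 neither require nor forbid censoring at new therapy, and they hand the details to the SAP. The protocol already stops counting responses at new therapy, so the SAP rule can be read as extending the same principle. It does, however, turn outcomes that the protocol text counts as events into censored observations, which is enough to merit a line in SAP 4.3.

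A reader might also infer that the SAP throws the post-transplant scans away. It does not. Tumor assessments are listed (SAP 5.9), on-study transplants are tabulated (5.6), subsequent therapies are listed with start dates (5.8.2), and the swimmer plot marks transplant (5.9.5). The scans are absent only from the Kaplan-Meier estimates. The mismatch with imaging is also specific to transplant, since scans stop after other new therapy. The protocol gives no reason for the transplant exception, and collecting data does not by itself define the analysis.

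Third, step 3 might be taken as evidence of bias. It is not. The model gives transplanted and other patients the same hazard before month 3, so censoring there is non-informative. What it shows is that the two rules estimate different quantities, with a sign that depends on an assumed hazard ratio. The transplant share is unsourced too, and inclusion criterion 3 already requires DLBCL patients to have failed or been intolerant to standard therapy, including transplant where eligible.

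These arguments stand and limit the point. They do not answer the boundary error or the absence of any analysis that follows patients through transplant.

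**Conclusion.** The boundary error is established from the text alone. It needs a first response, or first CR for RFS, documented on the very day new therapy starts. That will be rare and will hardly move a median, but the stated rule then returns an impossible value.

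The transplant point holds as a gap in the planned analyses. The SAP rule is a legitimate choice, but its effect cannot be seen from any planned estimate. How far the estimates would move, and in which direction, is unknown. The 9.4 to 11.7 month range for DoR is illustrative and rests on an assumed share (10 to 30%), timing (3 months) and hazard ratio (0.5 or 1.5); no figure was derived for RFS or PFS.

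DoR, RFS and PFS are secondary and descriptive in a single-arm study. CRR, and the sample size built on it, are unaffected. Early discontinuation (SAP 1 and 4) does not remove the point, because these endpoints are still to be reported for the patients treated.

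**What to change.** 1. In SAP 5.9.3, and through it 5.9.4, replace the censoring wording with that of PFS: "on or prior to subsequent therapy or procedure". The boundary case then gives 0 days, or 1 day with the added-day convention.
2. Keep the SAP rule as the main analysis. Add one sensitivity analysis each for DoR, RFS and PFS that does not censor at stem cell transplant but still censors at other new anti-cancer therapy, for which imaging stops. Describe it as a new sensitivity analysis, not as the protocol's rule: read literally, protocol 9.7.3 to 9.7.5 censor at no new therapy at all, so this version appears in neither document. Report how many patients are censored at stem cell transplant, CAR-T and other therapy.
3. Record the added new-therapy censoring in SAP 4.3. On its own this step is documentation only.

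The cost is a few lines of SAP text, one extra Kaplan-Meier run per endpoint and one count table. No new data collection is needed: post-transplant scans are scheduled in protocol 8.1 and start dates of subsequent therapy are already to be listed under SAP 5.8.2.

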#### **5.9.4 Relapse-Free Survival**

Relapse-Free Survival (RFS) is defined as the time from the documentation of CR to either disease progression (based on radiographic or clinical progression at EOT/EOS) or death due to any cause, whichever occurs first.

The censoring rules for DoR apply to RFS.

The RFS will be estimated by Kaplan-Meier method. The median RFS and its 95% two-sided CI will be presented by the IRC and the investigator, respectively.

#### **5.9.5 Progression-Free Survival**

Progression-Free Survival (PFS) is defined as the time from first dose of study drug until either disease progression (based on radiographic or clinical progression at EOT/EOS) or death due to any cause, whichever occurs first.

The censoring rules for PFS are as follow:

- For patients who are still alive at the time of analysis and without objective evidence of progression, patients will be censored at the last tumor assessment.
- For patients who receive subsequent anti-cancer therapy or procedure prior to disease progression or death, patients will be censored at the last tumor assessment on or prior to subsequent therapy or procedure.
- For patients have no post baseline tumor assessment, and have no disease progression or death, or receive subsequent anti-cancer therapy or procedure, patients will be censored at the first dose date of study drug.

- A sensitivity analysis might be considered: if a clinical progression or toxicity is observed without radiologic progression assessment confirmed, then the patient will be censored at the last tumor assessment.

The PFS will be estimated by Kaplan-Meier method. The median PFS and its 95% two-sided CI will be presented by the IRC and the investigator, respectively.

A swimmer plot will be displayed, including the points at which the criteria for response and progression by a specific manifestation were met (such as CR, PR, SD, PD, death, and stem cell transplant etc.).

### **5.9.6 Overall Survival**

Overall survival (OS) is defined as the time from first dose of study drug to the date of death from any cause.

For patients who are still alive or unknown at the time of analysis, patients will be censored at the date the patient was known to be alive.

The OS will be estimated by Kaplan-Meier method. The median OS and its 95% two-sided CI will be presented.

### **5.9.7 Subgroup Analyses**

Subgroup analyses may be performed for CRR, ORR, DoR, RFS, PFS, and OS using the following variables if appropriate:

- Demographic variables: age group, gender, race, and country
- Baseline disease characteristics: tumor staging and subtype
- Number of prior systemic therapies and response to prior systemic therapies

Other subgroup analysis factors may be evaluated as appropriate.

## **5.10 Safety Analyses**

All safety analyses will be based on the Safety Analysis Set.

### **5.10.1 Adverse Events**

#### **5.10.1.1 Analyses of Adverse Events**

An AE is defined as any untoward medical occurrence in a patient or clinical investigation subject administered a pharmaceutical product, which does not necessarily have to have a causal relationship with this treatment.

The definition of SAEs is referred to the Protocol section 8.2.1.

A treatment-emergent AE (TEAE) is defined as an AE that occurs or worsens in the period extending from the first dose of study drug to 30 days after the last dose of study drug in this study or start of a new anticancer therapy, whichever is earlier.

AEs will be coded according to MedDRA Version 22.0, and the severity of the toxicities will be graded according to the National Cancer Institute (NCI) Common Terminology Criteria for Adverse Events (CTCAE) Version 4.0, where applicable.

The summary of overall TEAEs includes:

- TEAEs
- Drug-related TEAEs (loncastuximab tesirine or ibrutinib)
- Grade  $\geq 3$  TEAEs
- Drug-related Grade  $\geq 3$  TEAEs (loncastuximab tesirine or ibrutinib)
- Serious Adverse Events (SAEs)
- Drug-related SAEs (loncastuximab tesirine or ibrutinib)
- TEAEs leading to dose delayed, reduced or interrupted (loncastuximab tesirine or ibrutinib)
- TEAEs leading to discontinuation of loncastuximab tesirine or ibrutinib
- TEAEs leading to death
- Infusion related reactions

The incidence of TEAEs will be summarized by system organ class (SOC) and preferred term (PT). A patient will be counted only once within a SOC and PT, even if the patient experienced more than one AE within a specific SOC and PT. Below TEAEs will be summarized in the same fashion:

- Drug-related TEAEs by SOC and PT
- Grade  $\geq 3$  TEAEs by SOC and PT
- Drug-related Grade  $\geq 3$  TEAEs by SOC and PT
- The most common TEAEs ( $\geq 10\%$  incidence) by PT
- TEAEs by SOC, PT and maximum CTCAE grade
- TEAEs by relationship to loncastuximab tesirine or ibrutinib, maximum CTCAE grade, SOC and PT

Listings of all AEs, including non-TEAEs, will be provided. Besides, TEAEs leading to dose reduced, delayed or interrupted (loncastuximab tesirine or ibrutinib), TEAEs leading to discontinuation of loncastuximab tesirine or ibrutinib, and TEAEs leading to death will also be provided.

Details on classification of AEs with missing or partial onset dates are provided in Section 6.

### **5.10.1.2 Dose-Limiting Toxities**

Definition of DLT is referred to the Protocol section 6.4.3.

DLTs will be summarized in each dose level in the dose-escalation part for the DLT-evaluable Analysis Set.

Listings of DLTs will be provided.

### **5.10.1.3 Serious Adverse Events**

A post-dose AE is defined as an AE during treatment that occurs or worsens from the first dose of study drug.

Below SAEs will be summarized in both TEAE and post-dose AE, respectively:

- SAEs by PT
- SAEs by SOC and PT
- SAEs by SOC, PT and maximum CTCAE grade

Listings of SAEs will be provided.

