Hematology and chemistry	8.3.5	X	X ⁴	X	X	X	X	
Coagulation and urinalysis	8.3.5	X						
HIV, HCV, HBV ⁵	8.3.5	X						
Pregnancy test, if applicable	8.3.6	X	X ⁴			X	X	X ⁶
12-lead ECG	8.3.7 Table 9& Table 10	X	X (pre-dose, EOI-, and 4 h post-dose)	X	X	X ⁸	X	

Table continued on next page.

	Protocol Section	Screening	Treatment Period					Follow-up Period (up to 2 years from EOT)
			Cycle 1 and Cycle 2 (C1 and C2) (3-week cycles)			C3 and beyond (up to 1 year after C1D1) (4-week cycles)		EOT
Premedication	6.7		D-1 to D2			X ⁹		
Loncastuximab tesirine administration ¹⁰	6.3.1		X			X ¹¹		
Ibrutinib administration	6.3.2		Daily × 21 days (concomitant administration only)			Daily × 28 days ¹²		
Loncastuximab tesirine PK sample	8.4.1 Table 12		X ¹⁰ (pre-dose, EOI, and 4 h post-dose)	X	X	X (C3, C5, C6, C7, C9, C10, and C11 pre-dose)	X	
Loncastuximab tesirine ADA sample ⁷	8.4.2 Table 12		X ¹⁰ (pre-dose)		X (C1 Only)	X ¹³	X ¹⁴	
PROs ¹⁵	8.5		X (pre-dose)			X (pre-dose)	X	X ¹⁶
Concomitant medications	6.8	From ICF signature date or D-14, whichever is earlier, until 30 days after last dose of study drug(s)						
Adverse events	8.2	AE/SAEs from ICF signature date until 30 days after last dose of study drug(s); thereafter, related SAEs only						
1 st new anticancer treatment	4.4						X	X
Survival	7.1						X	X

Abbreviations: ADA: anti-drug antibody; AE: adverse event; BP: blood pressure; C: Cycle; [REDACTED] ECG: electrocardiogram; ECOG: Eastern Cooperative Oncology Group; EOI: end of infusion; EOT: end of treatment; [REDACTED] h: hour; HBV: hepatitis B virus; HCV: hepatitis C virus; HIV: human immunodeficiency virus; HR: heart rate; ICF: informed consent form; PK: pharmacokinetics; PR: partial response; PRO: patient-reported outcome; RR: respiratory rate; SAE: serious AE; SD: stable disease; Temp: temperature

Visit Scheduling Windows:

- Treatment Period: Visit Day ± 2 days (excluding C1D1, which is the reference day).
- EOT: As soon as possible after decision to discontinue the study drug(s) but preferably within 30 days after last dose of study drug(s) unless a new anticancer treatment is planned to be administered before the 30 days, in which case EOT should be conducted before initiation of the new anticancer treatment.

- Follow-up Period: Visit Day \pm 14 days.
- Physical examination, ECOG, hematology, and chemistry can be performed within 24 hours prior to administration of study drug(s).

1 [REDACTED]

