8.2.2 Eliciting and Reporting Adverse Events/Serious Adverse Events

Patients will be instructed to contact the Investigator at any time after ICF signature if any symptoms develop. At each study visit, patients will be asked a non-leading question to elicit any medically related changes in their well-being. Patients may also report AEs voluntarily and they will be instructed to contact the Investigator between visits if any symptoms develop or worsen.

Adverse events (AEs) will be reported starting when the patient provides written informed consent. Clinically significant medical conditions present at the time of ICF signature will be reported as medical history. Clinically significant medical conditions that start or worsen after ICF signature will be reported as AEs.

All AE/SAEs, regardless of relationship to study drug, will be reported from the time the patient signs the ICF until 30 days after the last dose of study drug or the start of a new anti-cancer therapy, whichever occurs earlier; thereafter, only related SAEs will be reported with two exceptions:

1. Patients who have responded to loncastuximab tesirine and undergo SCT (either autologous or allogeneic) after permanent discontinuation of loncastuximab tesirine treatment without any intervening anti-cancer therapy. These patients will have the following safety information reported until 180 days' post-transplant regardless of relationship to loncastuximab tesirine:
 - a. Grade ≥ 3 AEs suggestive of hepatic toxicity, veno-occlusive disease/sinusoidal obstruction syndrome, graft-versus-host disease, infectious complications, prolonged cytopenia(s), and pulmonary toxicity
 - b. SAEs
 - c. Death
2. Patients who receive CAR-T therapy after permanent discontinuation of loncastuximab tesirine treatment will have the following safety information reported until 90 days after receiving CAR-T therapy regardless of relationship to loncastuximab tesirine:
 - a. Grade ≥ 3 AEs of cytokine release syndrome, encephalopathy, edema or effusion, rash, hepatic toxicity
 - b. SAEs
 - c. Death

Whenever possible, AEs should be reported as a diagnosis rather than individual signs and symptoms. If no diagnosis is available or has been identified, then the primary symptom is reported.

In general, the term 'disease progression' should not be used for reporting an AE/SAE. However, AEs/SAEs that are complications of disease progression should be reported.

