8.2.2.1 Adverse Events of Special Interest

Adverse Events of Special Interest (AESIs) are AEs of clinical importance that may require safety evaluation. For this study, events of major hemorrhage, as defined below, will be considered AESIs and must be reported to the pharmacovigilance department of the Sponsor or delegate (e.g., CRO) within 24 hours after site personnel first learn about the event. Reporting will occur through the EDC system.

Major Hemorrhage

Major hemorrhage is defined as any of the following:

- Any treatment-emergent hemorrhagic AE of Grade 3 or higher*
- Any treatment-emergent SAE of bleeding of any grade
- Any treatment-emergent CNS hemorrhage/hematoma of any grade

*All hemorrhagic events requiring transfusion of red blood cells (RBC) should be reported as Grade 3 or higher AE per CTCAE v4.03.

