### **5.10.1.5 Adverse Events of Special Interest**

Definition of adverse event of special interest (AESI) is referred to the Protocol section 8.2.2.1.

Below AESIs will be summarized in both TEAE and post-dose AE, respectively:

- AESIs by PT
- AESIs by SOC and PT
- AESIs by SOC, PT and maximum CTCAE grade

Listings of AESIs will be provided.

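### SAP 5.10.1.3 limits post-dose AEs to the treatment period, so the second set of SAE tables adds almost nothing and the late SAEs that Protocol 8.2.2 collects mostly get no summary counts

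*SAP*

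**What the plan says.** **Analysis.** SAP 5.10.1.3 plans two versions of each SAE table: "Below SAEs will be summarized in both TEAE and post-dose AE, respectively". The second set is defined as follows: "A post-dose AE is defined as an AE during treatment that occurs or worsens from the first dose of study drug". It has a start and no stated end date. SAP 5.10.1.1 ends the TEAE window at "30 days after the last dose of study drug in this study or start of a new anticancer therapy, whichever is earlier". SAP 5.10.1.5 doubles the AESI tables in the same way: "Below AESIs will be summarized in both TEAE and post-dose AE, respectively".

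**Collection.** Protocol 8.2.2 reports all AEs and SAEs to 30 days after last dose or to new anticancer therapy, whichever is earlier; "thereafter, only related SAEs will be reported with two exceptions". The first exception covers responders who go to transplant with no intervening anticancer therapy: "These patients will have the following safety information reported until 180 days" after transplant. The second covers patients who receive CAR-T, for 90 days. In both, listed Grade 3 or higher AEs, all SAEs and deaths are reported regardless of relationship.

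**Schedule.** The adverse-event row of Tables 1 and 2 reads: "AE/SAEs from ICF signature date until 30 days after last dose of study drug(s); thereafter, related SAEs only". It mentions neither exception, and it omits the cut-off at new anticancer therapy. The row does cite Section 8.2.

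**AESIs.** Protocol 8.2.2.1 makes treatment emergence part of each of the three major-hemorrhage criteria. The first is "Any treatment-emergent hemorrhagic AE of Grade 3 or higher".

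**The concern.** A second set of SAE tables is worth producing only if it reaches beyond the TEAE window. The definition points the other way, because it confines the set to treatment. The protocol chose to follow patients who go on to transplant or CAR-T after a CD19-directed drug, and to keep collecting related SAEs. A reader of the study report who sees a table headed post-dose SAEs would expect those events to be counted in it. Listings keep the individual events but give no rates. The frequency and severity of AEs and SAEs is a Phase 1 primary endpoint and a Phase 2 secondary endpoint. With the every-cycle cohort not enrolled (SAP 4), safety carries more of the report.

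**Working it through.** The plan gives no figure to reproduce. The check compares windows, counted in days after last dose of study drug.

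**Inputs**
- TEAE end: day 30, or the start of new anticancer therapy if earlier (SAP 5.10.1.1).
- Post-dose end, read as written: the end of treatment. Taken strictly this is day 0. By Protocol 4.3 the Treatment Period runs to the end-of-treatment visit, which Protocol 4.4 places preferably within 30 days of last dose and before any new anticancer treatment.
- Required reporting: from day x to x + 180 (transplant) or x + 90 (CAR-T), where x is the day of the procedure (Protocol 8.2.2).
- x is not given in the documents. Assumed range: 1 to 90 days.

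**Step 1: is the second set wider than the first?** If the end-of-treatment visit falls on day e, with e at most 30 and before any new therapy, the post-dose set ends at or before the TEAE end and adds nothing. If e is later than 30, it adds e − 30 days. The gain is therefore nil or short.

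**Step 2: reporting days outside both sets when the procedure counts as new anticancer therapy.** The TEAE window then ends no later than day x. Required days inside it: 0. Outside both sets: 180 − 0 = 180 of 180 (transplant) and 90 − 0 = 90 of 90 (CAR-T), for every x.

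**Step 3: the same when the procedure does not count.** The TEAE window runs to day 30, so the days inside it are max(0, 30 − x).

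| x | days inside TEAE window | transplant days outside | CAR-T days outside |
|---|---|---|---|
| 1 | 29 | 180 − 29 = 151 | 90 − 29 = 61 |
| 14 | 16 | 180 − 16 = 164 | 90 − 16 = 74 |
| 30, 60, 90 | 0 | 180 | 90 |

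These results hold for an end-of-treatment visit by day 30 and, in Step 2, before the procedure. A later visit would recover a few days.

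**Step 4: which case applies to transplant?** The documents do not settle it. SAP 5.8.2 lists transplant among subsequent therapies or procedures. The TEAE definition names therapy only. The follow-up imaging rule in Protocol 8.1 makes stem cell transplant an exception to other anticancer therapy.

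**Step 5: related SAEs.** Those starting after day 30 lie outside the TEAE window and, unless the end-of-treatment visit is later still, outside the post-dose set.

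**Step 6: effect of the change.** If the post-dose set runs to the end of the 8.2.2 reporting period, 0 of 180 and 0 of 90 days fall outside the SAE tables.

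**The case against.** The best reply is that the definition states no end date, and that setting it beside the TEAE set implies an open-ended intent. On that reading no late SAE is lost. The intent is plausible, but the words say otherwise: the protocol bounds the Treatment Period, and two programmers could produce different tables from the same sentence. The point therefore stands as a defect of wording with a consequence, and not as proof that the sponsor means to exclude these events.

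Several stronger inferences are tempting, and the documents do not support them.
- *Late events disappear from every safety output.* They do not. SAP 5.10.1.1, 5.10.1.3 and 5.10.1.4 list all AEs including non-TEAEs, SAEs and deaths. Deaths also count in overall survival, and SAP 8.1.1 treats AEs with partial or missing dates as TEAEs.
- *Post-dose counts can never exceed TEAE counts.* A late end-of-treatment visit could make the post-dose set slightly longer.
- *The AESI tables lose late bleeds.* By protocol definition a bleed that is not treatment-emergent is not an AESI. The second AESI table is redundant, and widening the definition in the SAP would create a conflict with the protocol.
- *The wording is why non-serious Grade 3 or higher late AEs have no table.* The reason is that post-dose tables are planned only for SAEs and AESIs.
- *The Schedule of Events gap removes events from the SAP tables.* It does not. It is a separate risk to data collection, reduced by the row's reference to Section 8.2.

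It is also fair to say that Protocol 8.2.2 requires reporting and does not require tabulation, and that Protocol 9.8.1 puts the focus on TEAEs. That makes dedicated post-transplant and post-CAR-T tables a matter of choice. It does not excuse a second SAE set that adds almost nothing.

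**Conclusion.** The concern holds in this form. As written, the post-dose SAE tables add almost nothing to the TEAE tables. Late SAEs required by Protocol 8.2.2 would mostly have listings but no summary counts, apart from AEs with partial or missing dates. Per affected patient, the reporting time outside both sets is 151 to 180 of 180 days after transplant and 61 to 90 of 90 days after CAR-T. It is the full period if the procedure ends the TEAE window. These figures rest on the literal reading, on treatment ending by day 30 and before the procedure where that ends the TEAE window, and on an assumed gap of 1 to 90 days. The transplant window applies only to responders without intervening therapy. The documents do not say how many patients are affected, so no effect on SAE rates can be calculated. Separately, the adverse-event row of Schedule of Events Tables 1 and 2 is inconsistent with Protocol 8.2.2. The change should be made before database lock.

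**What to change.** 1. **SAP 5.10.1.3:** delete the words *during treatment*. Define a post-dose AE as any AE that starts or worsens on or after the first dose, through the end of the Protocol 8.2.2 reporting period. Section 8.2.2 names no last date for related SAEs, so the SAP should state one.
2. **SAP 5.10.1.1:** state whether transplant ends the TEAE window.
3. **Table labels:** mark events after transplant, CAR-T or other new therapy as potentially confounded by that therapy.
4. **SAP 5.10.1.5:** drop the post-dose AESI tables as redundant and leave the protocol's AESI definition unchanged.
5. **Schedule of Events, Tables 1 and 2:** reconcile the adverse-event row with Protocol 8.2.2 on the new-therapy cut-off and both exceptions.
6. **Optional:** short summaries of the post-transplant and post-CAR-T Grade 3 or higher AEs, with the patients covered by each exception as denominator. Item 1 alone does not bring in the non-serious events.

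The cost is a few lines of SAP text and a correction to the schedule. No new data are needed, because Protocol 8.2.2 already requires them, and one set of tables is removed. The downside is that late events of uncertain attribution enter a table, which the labels in item 3 address.
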